1.25 EFFICACY ASSESSMENTS

The primary outcome measure is olfactory ability at 6 weeks and 18 weeks, measured via the SIT. There are only 3 procedures involved in the study to assess efficacy: (1) SIT measures (2) Administration of study medication or placebo, (3) the QOD quality of life questionnaire.

- The SIT is a self-administered 40-item test involving microencapsulated (scratch-and-sniff) odors with a forced-choice design. There are 4 booklets with 10 questions each, asking the subject to identify which of 4 answers best described the odor. Total scores are categorized, based on normative data, as normal, mild hyposmia, moderate hyposmia, severe hposmia, total anosmia, or probable malingering. The test was developed at University of Pennsylvania as part of an NIH-funded program project and is widely used as a standard assessment of olfactory function.
- The QOD is a validated olfactory-specific quality of life questionnaire and is attached.

1.26 SAFETY AND OTHER ASSESSMENTS

The potential patient safety issue for the study is the possibility of adverse reaction to study medication. The dosage regimen we are using has been used as standard for this drug, as prescribed for metered dose nasal spray for rhinitis or nasal polyps. Patients will receive instructions and contact information to inform the coordinator or PI promptly of any potential problems. At follow up visit, we will collect any comments or notes regarding possible side effects.

1.27 ADVERSE EVENTS AND SERIOUS ADVERSE EVENTS

1.27.1 DEFINITION OF ADVERSE EVENTS (AE)

Adverse event means any untoward medical occurrence associated with the use of an intervention in humans, whether or not considered intervention-related (21 CFR 312.32 (a)).

1.27.2 DEFINITION OF SERIOUS ADVERSE EVENTS (SAE)

An adverse event (AE) or suspected adverse reaction is considered "serious" if, in the view of either the investigator or sponsor, it results in any of the following outcomes: death, a life-threatening adverse event, inpatient hospitalization or prolongation of existing hospitalization, a persistent or significant incapacity or substantial disruption of the ability to conduct normal life functions, or a congenital anomaly/birth defect. Important medical events that may not result in death, be life-threatening, or require hospitalization may be considered serious when, based upon appropriate medical judgment, they may jeopardize the participant and may require medical or surgical intervention to prevent one of the outcomes listed in this definition. Examples of such medical events include allergic reaction requiring intensive treatment in an emergency room or at home.

1.27.3 CLASSIFICATION OF AN ADVERSE EVENT

1.27.3.1 SEVERITY OF EVENT

For adverse events (AEs) not included in the protocol defined grading system, the following guidelines will be used to describe severity.

- **Mild** – Events require minimal or no treatment and do not interfere with the participant’s daily activities.
- **Moderate** – Events result in a low level of inconvenience or concern with the therapeutic measures. Moderate events may cause some interference with functioning.
- **Severe** – Events interrupt a participant’s usual daily activity and may require systemic drug therapy or other treatment. Severe events are usually potentially life-threatening or incapacitating. Of note, the term “severe” does not necessarily equate to “serious”.

1.27.3.2 RELATIONSHIP TO STUDY INTERVENTION

All adverse events (AEs) must have their relationship to study intervention assessed by the clinician who examines and evaluates the participant based on temporal relationship and his/her clinical judgment. The degree of certainty about causality will be graded using the categories below. In a clinical trial, the study product must always be suspect.

- **Related** – The AE is known to occur with the study intervention, there is a reasonable possibility that the study intervention caused the AE, or there is a temporal relationship between the study intervention and event. Reasonable possibility means that there is evidence to suggest a causal relationship between the study intervention and the AE.
- **Not Related** – There is not a reasonable possibility that the administration of the study intervention caused the event, there is no temporal relationship between the study intervention and event onset, or an alternate etiology has been established.

1.27.3.3 EXPECTEDNESS

PI will be responsible for determining whether an adverse event (AE) is expected or unexpected. An AE will be considered unexpected if the nature, severity, or frequency of the event is not consistent with the risk information previously described for the study intervention.

1.27.4 TIME PERIOD AND FREQUENCY FOR EVENT ASSESSMENT AND FOLLOW-UP

The occurrence of an adverse event (AE) or serious adverse event (SAE) may come to the attention of study personnel during study visits and interviews of a study participant presenting for medical care, or upon review by a study monitor.

All AEs including local and systemic reactions not meeting the criteria for SAEs will be captured on the appropriate case report form (CRF). Information to be collected includes event description, time of onset, clinician’s assessment of severity, relationship to study product (assessed only by those with the training and authority to make a diagnosis), and time of resolution/stabilization of the event. All AEs

occurring while on study must be documented appropriately regardless of relationship. All AEs will be followed to adequate resolution.

Any medical condition that is present at the time that the participant is screened will be considered as baseline and not reported as an AE. However, if the study participant's condition deteriorates at any time during the study, it will be recorded as an AE.

Changes in the severity of an AE will be documented to allow an assessment of the duration of the event at each level of severity to be performed. AEs characterized as intermittent require documentation of onset and duration of each episode.

PI will record all reportable events with start dates occurring any time after informed consent is obtained until 7 (for non-serious AEs) or 30 days (for SAEs) after the last day of study participation. At each study visit, the investigator will inquire about the occurrence of AE/SAEs since the last visit. Events will be followed for outcome information until resolution or stabilization.

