1.22 DISCONTINUATION OF STUDY INTERVENTION

If a patient notes a possible adverse effect, such as allergic reaction to study medication, we will discontinue study medication. Any new clinically relevant finding will be reported as an adverse event (AE). Because the outpatient course of study medication is only 6 days, we will not restart study medication in that short timeframe and instead will withdraw the patient from this study. Such patients will still be offered planned follow up and the planned outcome measures will still be collected.

The data to be collected at the time of study intervention discontinuation will include the following:

- Details of possible adverse event, and appropriate care as indicated (for example ER assessment).

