1.23 PARTICIPANT DISCONTINUATION/WITHDRAWAL FROM THE STUDY

Participants are free to withdraw from participation in the study at any time upon request.

An investigator may discontinue or withdraw a participant from the study for the following reasons:

- If any clinical adverse event (AE), laboratory abnormality, or other medical condition or situation occurs such that continued participation in the study would not be in the best interest of the participant
- If the participant meets an exclusion criterion (either newly developed or not previously recognized) that precludes further study participation

The reason for participant discontinuation or withdrawal from the study will be recorded on the Case Report Form (CRF). Subjects who sign the informed consent form and are randomized but do not receive the study intervention may be replaced. Subjects who sign the informed consent form, and are randomized and receive the study intervention, and subsequently withdraw, or are withdrawn or discontinued from the study, will be replaced. Patients who do not complete the full course of study drug/placebo will be noted in the results tables, and they will not be included in the statistical analysis of outcome measures, since this is a simple comparison of SIT score between patients receiving 2 applications of drug versus placebo.

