1.30 SAMPLE SIZE DETERMINATION

Number of participants to enroll to have adequate power to test the key hypotheses for the study:

Placebo group: 10

Treatment group: 10

- Target study sample size: 10 subjects in each arm, 20 subjects total. Anticipated number to be screened in order to reach the target enrollment: 50 subjects
- *Outcome measure used for calculations: SIT score*
- *Test statistic: t-test*
- *Null and alternative hypotheses:*
 - Null hypothesis: There is no difference in SIT score with drug treatment or placebo.
 - Alternative hypothesis: NAC treatment results in improved SIT score.
- *Type I error rate (alpha): 0.05*
- *Power level: 0.8*
- *Assumed mean and variance:*
 - Placebo group, μ_1 : SIT=24 \pm 4
 - Treatment group, μ_2 : SIT=29 \pm 4

Reference: "Hypothesis Testing: Two-Sample Inference - Estimation of Sample Size and Power for Comparing Two Means" in Rosner, Bernard Fundamentals of Biostatistics, Belmont, Calif. : Duxbury Press, [1995].

SIT score of 24 is used for the placebo group because this is a score categorized as severe hyposmia (reduced olfaction). Based on published reports and our experience with long-COVID hyposmia subjects, we anticipate identifying and enrolling patients with a mean score of approximately 24 and a variance of approximately 4.

In terms of estimated possible improvement in SIT score with drug treatment, we have chosen an increase of 5 ± 4 points, because a jump of more than a few points on a repeat SIT test after one month is considered to be greater than just random chance³; (and [name], *personal communication*). There are no published data available for specifically measuring olfactory change following treatment with beclomethasone applied to the olfactory cleft topically for post-viral hyposia.

- *Anticipated impact of dropout rates, withdrawal, missing data, etc. on study power:* to compensate for such issues, we have increased our sample size by 1 subject per group.
- *Secondary endpoint:* We have included a secondary endpoint to measure quality of life via a validated questionnaire (QOD). We have no specific guides for mean or variance for the questionnaire in terms of possible beclomethasone or placebo treatment, so no calculations are possible. Nonetheless, a simple questionnaire poses no cost or risk, such that we see no reason to not collect these data.

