1.32.2 ANALYSIS OF THE PRIMARY EFFICACY ENDPOINT(S)

Primary endpoint is SIT score at 6 weeks and 18 weeks.

Placebo and drug-treated groups will be compared. SIT (mean \pm sd) will be compared via two-tailed t-test. SIT scores may range from 0-40, and normal scores are well-established. An assignment of normosmia, mild hyposmia, moderate hyposmia, severe hyposmia, anosmia, or probable malingering can be made based on SIT score.

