1.32.4 SAFETY ANALYSES

There is no formal safety endpoint being evaluated. AEs will be counted per event and will be presented as number of AEs and severity.

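### Reported worsening of smell can count as an adverse event, stop treatment and remove a randomized participant from the SIT comparison, although the outcome is still collected

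*Combined protocol and SAP*

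**What the plan says.** Section 1.27.4 sets the baseline rule: "Any medical condition that is present at the time that the participant is screened will be considered as baseline and not reported as an AE". It adds that if the participant's "condition deteriorates at any time during the study, it will be recorded as an AE". Neither sentence mentions the study condition, and 1.27.8 (events of special interest) is marked not applicable.

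Post-COVID hyposmia is the entry condition (1.12), and olfaction is the efficacy outcome. Section 1.32.2 states: "Primary endpoint is SIT score at 6 weeks and 18 weeks".

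Four other sections bear on what follows a report of worse smell:

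- **1.27.3.2 (relatedness).** One of the alternatives sufficient for a related event is timing: "or there is a temporal relationship between the study intervention and event".
- **1.22 (stopping).** "If a patient notes a possible adverse effect, such as allergic reaction to study medication, we will discontinue study medication". The patient is then withdrawn, but follow-up is offered and the planned outcomes are still collected.
- **1.23 (analysis).** Of patients without the full course it says "they will not be included in the statistical analysis of outcome measures". Treated participants who are later withdrawn are replaced.
- **1.31 (populations).** The only analysis set named is intention-to-treat, defined as all randomized participants, 10 per arm.

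For safety, 1.32.4 plans one summary: "AEs will be counted per event and will be presented as number of AEs and severity". It also says that there is no formal safety endpoint.

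**The concern.** The same experience, a participant's smell getting worse, is both a loss on the efficacy outcome and a recordable AE. This matters in two places.

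The more important one is the primary comparison. A participant who reports worse smell after the first application can be stopped under 1.22 and then excluded under 1.23. That exclusion depends on an early form of the outcome being compared. Replacement restores the number of patients but not the randomized comparison. If early worsening is more common in one arm, that arm loses more of its likely poor responders and its mean SIT is too high.

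The lesser one is the AE table. Its single total would mix worsening of the disease under study with other events, such as drug reactions or injury at placement.

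**Working it through.** **1. The chain, section by section.**

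| Step | Section | Stated or inferred |
|---|---|---|
| Worsening of a condition present at screening is an AE | 1.27.4 | Stated; hyposmia not exempted |
| Worse smell enters the AE count | 1.32.4 | Follows from the step above |
| Timing alone can make the event related | 1.27.3.2 | Stated |
| Worse smell is a possible adverse effect that stops medication | 1.22 | Inferred; the only example is an allergic reaction, and smell is neither named nor excluded |
| Incomplete course leaves the outcome analysis; withdrawn treated patients are replaced | 1.23 | Stated |
| Outcomes are still collected | 1.22 | Stated |
| All randomized participants form the analysis set | 1.31 | Stated; conflicts with 1.23 |

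**2. When the chain can run.** The schedule of activities (1.3) has SIT at screening, week 6 and week 18, and an AE review but no SIT or QOD at Day 14. The course is two applications, Day 0 and Day 14 in that schedule. Only worsening between them can leave the course incomplete, and in that interval only the patient's own report can reveal it.

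**3. The plan's own figure.** The concern disputes no number in the plan; the one it bears on is the sample size in 1.30: difference 29 − 24 = 5, SD 4, alpha 0.05, power 0.8, one extra patient per arm. A one-sided t-test needs 8.68, so 9 per arm, and 9 + 1 = 10 matches. The planned two-tailed t-test needs 11.09, so 12 per arm before the extra patient. Two-sided power with noncentral t at a standardized difference of 5/4 = 1.25:

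| Analyzed per arm | Power |
|---|---|
| 10 and 10 | 75.3% |
| 10 and 9 | 72.7% |
| 10 and 8 | 69.7% |
| 9 and 9 | 70.2% |
| 8 and 8 | 64.3% |

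These are the losses if excluded patients are not replaced.

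**4. Shift if one patient leaves one arm of 10.** The expected minimum of 10 standard normal values is −1.539.

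- Worst case, where the patient who leaves would have scored lowest: 1.539 / 9 = 0.171 SD, and 0.171 × 4 = 0.68 points, or 0.68 / 5 = 14% of the target.
- The patient who leaves has the lowest early state, with an assumed correlation of 0.5 between early state and final SIT: 0.5 × 0.68 = 0.34 points.
- The same, with an average replacement as 1.23 requires: 0.5 × 1.539 × 4 / 10 = 0.31 points.

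**5. Shift when both arms can lose patients.** A simulation assumed 10 per arm, final SIT SD 4, early change SD 3, correlation 0.5, exclusion of everyone with an early drop beyond 3 or 5 points, and no replacement.

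| Early change on drug relative to placebo | Error in SIT difference (drug minus placebo) |
|---|---|
| Equal | about 0; type I error about 5% |
| 2 points worse | 0.4 to 0.7 too high |
| 2 to 2.5 points better | 0.1 to 0.4 too low |

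The documents give no rate of early worsening, so every input in steps 4 and 5 except the SD of 4 and the 10 per arm is an assumption.

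**The case against.** Recording an AE under 1.27.4 stops nothing. The stop comes from 1.22, whose one example is an allergic reaction. This stands: the link to 1.23 is an inference, and the documents never say that worse smell triggers it. But neither do they exclude it, and 1.27.3.2 lets timing alone make an event related.

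The conflict between 1.23 and 1.31 exists for any cause of an incomplete course. That also stands. Reported worsening of smell is the case where exclusion is most directly tied to the outcome, and one reconciliation settles both.

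A reader might infer that every small fall in SIT becomes an AE, filling the placebo arm with 8 to 9 events (20 tests × a probability of 0.40 to 0.45 of a drop of at least 1 point, for SD of change 2 to 4 and no mean change). The documents do not support this. Section 1.27.4 speaks of a participant's condition, with a clinician's assessment of severity, not of a test score. It follows one event to resolution or stabilization, so a persistent fall should not be counted twice. Section 1.30 itself says that "a jump of more than a few points on a repeat SIT test after one month is considered to be greater than just random chance", which argues against treating a 1-point fall as deterioration. With the same SDs and a correlation of 0.5 between the two tests, counting patients gives 5.6 to 6.2 of 10 on placebo with any drop and 0.7 to 3.0 with a drop of 4 or more. Even these are counts of score changes, not forecasts of AEs.

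A reader might also infer that worse smell has no place among AEs. Section 1.7.1 lists tissue injury during endoscopic placement as a risk, so worsening may be a genuine local harm. Taking it out of AE recording would lose severity, relatedness and follow-up. The per-event descriptions (1.27.4) and the individual patient table (1.32.8) already allow smell events to be picked out.

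**Conclusion.** The concern holds for the analysis population and, in a small way, for the AE table. The plan leaves open a route by which reported worsening of smell before the second application removes a randomized participant from the primary comparison, although that participant's SIT is still collected and 1.31 calls for everyone randomized.

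The likely size is modest: about 0.3 SIT points if one patient leaves one arm at a correlation of 0.5, and 0.68 at worst. There is no bias in the simulated case of equal early worsening, and the direction otherwise depends on which arm worsens more.

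It would go too far to say that the AE totals cannot be read as safety, or that the type I error is materially inflated. The first fails because events are described individually and no test rests on the total. The second fails because the simulated error with no true effect stayed between about 5% and 6%, even with unequal early worsening.

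**What to change.** Reconcile 1.22, 1.23 and 1.31 with wording such as: The primary SIT comparison includes every randomized participant with a SIT score at the visit concerned, in the arm assigned, whether or not both applications were given. This includes participants who stopped after reporting worse smell. A comparison restricted to participants who received both applications is a sensitivity analysis.

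In 1.32.4, add: Worsening of smell is recorded as an AE with severity and relatedness, and is shown by arm on its own line, apart from other AEs.

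The sections should also say whether reported worsening of smell falls under the trigger in 1.22. That is for the investigators to settle, and no change to the clinical stopping rule is proposed.

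The cost is one table line and a primary comparison that includes participants with an incomplete course, which may dilute the estimated effect of two applications. The sensitivity analysis covers that question. No new data are needed. The change should be made before unblinding.

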1.27.5 ADVERSE EVENT REPORTING

Adverse Event reporting will adhere to all established guidelines, as described below.

1.27.6 SERIOUS ADVERSE EVENT REPORTING

The study clinician will immediately report to the Duke Human Subjects Research Office any serious adverse event, whether or not considered study intervention related, including those listed in the protocol or investigator brochure and must include an assessment of whether there is a reasonable possibility that the study intervention caused the event. Study endpoints that are serious adverse events (e.g., all-cause mortality) must be reported in accordance with the protocol unless there is evidence suggesting a causal relationship between the study intervention and the event (e.g., death from anaphylaxis). In that case, the investigator must immediately report the event to the sponsor.

All serious adverse events (SAEs) will be followed until satisfactory resolution or until the site investigator deems the event to be chronic or the participant is stable.

1.27.7 REPORTING EVENTS TO PARTICIPANTS

Any subjects who have not yet completed their first follow up visit will be contacted by phone to inform them of any Serious Adverse Events, if any occur.

1.27.8 EVENTS OF SPECIAL INTEREST

Not Applicable

1.27.9 REPORTING OF PREGNANCY

N/A

1.28 UNANTICIPATED PROBLEMS

1.28.1 DEFINITION OF UNANTICIPATED PROBLEMS (UP)

Unanticipated problems involving risks to participants or others include, in general, any incident, experience, or outcome that meets all of the following criteria:

- Unexpected in terms of nature, severity, or frequency given (a) the research procedures that are described in the protocol-related documents, such as the Institutional Review Board (IRB)-approved research protocol and informed consent document; and (b) the characteristics of the participant population being studied;
- Related or possibly related to participation in the research (“possibly related” means there is a reasonable possibility that the incident, experience, or outcome may have been caused by the procedures involved in the research); and
- Suggests that the research places participants or others at a greater risk of harm (including physical, psychological, economic, or social harm) than was previously known or recognized.

1.28.2 UNANTICIPATED PROBLEM REPORTING

The investigator will report unanticipated problems (UPs) to the reviewing Institutional Review Board (IRB) and to the Data Coordinating Center (DCC)/lead principal investigator (PI). The UP report will include the following information:

- Protocol identifying information: protocol title and number, PI’s name, and the IRB project number;
- A detailed description of the event, incident, experience, or outcome;
- An explanation of the basis for determining that the event, incident, experience, or outcome represents an UP;
- A description of any changes to the protocol or other corrective actions that have been taken or are proposed in response to the UP.

To satisfy the requirement for prompt reporting, UPs will be reported using the following timeline:

- UPs that are serious adverse events (SAEs) will be reported to the IRB and to the DCC/study sponsor within 5 days of the investigator becoming aware of the event.
- Any other UP will be reported to the IRB and to the DCC/study sponsor within 1 week of the investigator becoming aware of the problem.
- All UPs should be reported to appropriate institutional officials (as required by an institution’s written reporting procedures), the supporting agency head (or designee), within 1 week of the IRB’s receipt of the report of the problem from the investigator.

